8.6.4. Body Weight, Height and BMI

Height, weight, and calculation of BMI will be performed as detailed in the SoE in Section [1.3](#).

8.6.5. Physical Examinations

Physical examinations will be performed as detailed in the SoE in Section [1.3](#).

A full physical examination should include an evaluation of the head, eyes, ears, nose, and throat and the cardiovascular, dermatological, musculoskeletal, respiratory, GI, and neurological systems.

In the targeted (symptom driven) physical examination, a physician will assess the subject; if the subject reports feeling unwell or has ongoing AEs, then the physician will examine the appropriate body system(s) if required.

Any abnormality in physical examination identified at baseline and any abnormalities that are changes from baseline should be recorded. New or worsened clinically relevant abnormalities should be recorded as AEs.

8.6.6. Vital Signs

Vital signs will be performed as detailed in the SoE in Section [1.3](#).

Allowable time windows for vital sign assessments are provided in Section [10.7](#).

Vital signs will include the measurements of respiratory rate, heart rate, systolic and diastolic blood pressures, and temperature. Vital signs will be measured after the subject has rested in a supine position for at least 5 minutes, prior to laboratory draws, and at the same time points as ECGs.

8.6.7. Electrocardiograms

Electrocardiograms will be performed as detailed in the SoE in Section [1.3](#).

Allowable time windows for ECGs are provided in Section [10.7](#).

Triplet 12-lead ECGs (approximately 2 minutes apart) will be recorded for every subject. The ECG will be measured after the subject has rested in a supine position for at least 5 minutes. At any visit during which a subject exhibits a heart rate ≤ 50 bpm or other clinical indications for ECG, the ECG will be repeated in triplicate. Abnormal, clinically relevant findings occurring post-baseline will be reported as AEs. Whether or not the measurement is performed, the date the ECG is performed, heart rate, PR interval, RR interval, QRS amplitude, QT interval, QTcF interval, and results will be recorded.

8.7. Pharmacogenomic (Inherited Genetic) Analysis

A mandatory single blood sample for pharmacogenomic (PGx) analysis will be collected pre-dose from each enrolled subject. Detailed instructions for the collection, handling, and

shipping of samples are outlined in the Laboratory Specifications Document as detailed in the CSPM.

Genetic analyses will not be performed on blood samples collected for PK or safety assessments. Subject confidentiality will be maintained; data will be decoded and the testing lab will not have traceability information.

Deoxyribonucleic acid (DNA) samples will be stored, as outlined in Section [8.7.2](#), for performing possible PGx analysis in the future, otherwise all remaining DNA samples will be destroyed.

8.7.1. Banking of Specimens for Inherited Genetic Analysis

Procedures for the long-term preservation (banking) of blood and/or DNA specimens extracted from subjects' blood samples for each subject that consented are described in the CSPM.

The banked samples may be analyzed for genes involved in absorption, distribution, metabolism, elimination, safety, and efficacy of quizartinib. Additionally, samples may be analyzed for genes involved in quizartinib related signaling pathways, or to examine diseases or physiologic processes related to quizartinib. DNA samples will not be immortalized or sold to anyone. This information may be useful in increasing the knowledge of differences among individuals in the way they respond to the study drug, as well as helping in the development of new drugs or improvement of existing drugs.

8.7.2. Storage and Disposal of Specimens

Banked DNA samples will be stored for a maximum of 15 years (at Thermo Fisher Scientific, United States of America [USA] or other provider selected by the Sponsor) after the finalization of the clinical study report for this protocol. These specimens will be kept for pharmacogenetic analysis in case new genomic or genetic information is obtained in the future regarding the response (PK or pharmacodynamic) to quizartinib, or in case serious adverse drug reactions are noted in a clinical study and pharmacogenetic analysis is to be conducted for investigation into the cause.

During the storage period, the samples will be coded with labels having no personal information and will not be immortalized or sold to anyone. Subjects will have the right to withdraw consent and have their sample destroyed at any time. However, the data will not be discarded if analysis has been completed before the subject withdraws consent.

The samples will be destroyed in line with Thermo Fisher Scientific's/the provider's SOPs and in line with local regulations.

8.7.3. Disclosure of the Results of Future Pharmacogenetic Analysis

Because the nature and value of future pharmacogenetic analysis cannot be known at this time, any results obtained from research involving pharmacogenetic samples will not be disclosed to the subject or Investigators now or in the future.

9. STATISTICAL CONSIDERATIONS

9.1. Statistical Hypothesis

This is not a hypothesis testing study.

9.2. Sample Size Determination

The number of subjects planned for this study was not based on statistical power calculations. 8 subjects will be enrolled in the study to target at least 6 subjects to complete the PK evaluation (i.e., to allow for withdrawal or non-PK evaluability in up to 2 dosed subjects).

9.3. Exposure and Compliance

As the dose administration is under the control of the study site, compliance to study medication will not be an issue. Study drug administration will be summarized by subject, treatment, and time of dosing.

9.4. Population for Analysis Sets

9.4.1. Pharmacokinetic Population

The PK Analysis Population is defined as all subjects who received the study drug and have a corresponding measurable concentration. The PK Analysis Population will be used for the descriptive statistics of concentration data and to generate mean and individual concentration time profiles.

The PK Evaluable Population includes all subjects who are evaluable as defined below and have a sufficient number of measurable concentrations to estimate PK parameters. An evaluable subject is defined as a subject who has received both the oral and IV microtracer IMPs (i.e., a single, oral dose of 60 mg quizartinib dihydrochloride tablets [2 x 30 mg tablets] and an IV administration of 50 μ g 14C-quizartinib solution for infusion 10 μ g/mL containing NMT 22.84 kBq 14C in 5 mL [NMT 4.6 kBq/mL] over 15 minutes at 4 hours post-oral dose) and has sufficient samples for evaluation of plasma PK parameters. The PK Evaluable Population will be used for summaries of PK parameter estimates.

Additional exclusions and flags may be required to address relevant protocol deviations and AEs.

Specific exclusions may be made for the fecal and urine datasets in relation to missing and/spilled samples.

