4.3. Justification for Dose

The quizartinib dose of 60 mg is the approved dose for relapse/refractory AML in Japan and the maximum maintenance therapeutic dose currently being investigated for AML first-line therapy in the QuANTUM-First study NCT02668653 (7).

This an absolute bioavailability study where an IV microdose of quizartinib containing microtracer amounts of ¹⁴C is administered following administration of an oral dose of quizartinib to determine the bioavailability of the oral dose compared with the IV dose. According to the International Council for Harmonisation of Technical Requirements for Pharmaceuticals for Human Use (ICH) M3 guidance, a microdose is a dose that is <1/100th of the pharmacologically active dose up to a maximum of 100 µg. In addition, to ensure that the IV

microdose does not contribute significantly to the exposure following oral dosing, the IV dose is reduced further and in this study will be 1/1200th of the oral dose.

The IV microtracer dose has been selected to contain NMT 22.84 kBq. This has been selected as it is below the standard radioactive dose used in this type of study, and will be sufficient to meet the objectives, but contains a low enough amount of radioactivity so as not to cause a significant risk to the subjects.

Therefore the IV dose for this study will be 50 µg ¹⁴C-quizartinib containing NMT 22.84 kBq. This IV dose is 1/1200th of the oral dose administered in this study and <1/100th of the likely therapeutic dose, and hence is an appropriate 'IV microtracer dose'.

To ensure that the [¹⁴C] drug product does not exceed the limit for radioactive dose approved by ARSAC, the target specific activity of the drug substance will be set at 90% of 90% of the threshold radioactive dosing limit. This will allow for tolerances in the manufacturing processes for both drug substance and drug product thereby providing continued assurance for compliance with the ARSAC-approved limit for drug product radioactivity dose.

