9.4.2. Safety Population

The safety analysis will be conducted using the Safety Population defined as all subjects who receive at least 1 dose of quizartinib.

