9.5.2.2. Statistical Analysis of Pharmacokinetic Endpoints

The PK Analysis Population and the PK Evaluable Population will be used for PK analyses, details of which will be presented in the SAP.

Using the PK Analysis Population, descriptive statistics will be presented for plasma and whole blood concentrations at each sampling time point. Plasma concentration-time data will be analyzed using non-compartmental methods. Whole blood-to-plasma quizartinib and AC886 concentration ratios (Kbp) will also be calculated at each sampling time point.

The PK Evaluable Population will be used for the calculation and summaries of the PK parameters listed in Section 9.5.2.1.

Note that when percent extrapolated AUC (AUCextr (%)) is greater than 20%, AUCinf and related parameters will be summarized with and without those individuals having >20% AUCextr (%). For the primary analysis, including calculation of absolute bioavailability (F), individuals having >20% AUCextr (%) will be excluded. An additional subset may be required in order to include individuals having >20% AUCextr (%); this will be documented in the clinical study report.

Absolute bioavailability (F) will be calculated based on the dose-normalized quizartinib plasma AUC_{inf} after the oral dose (data from the cold assay [i.e., ¹²C-quizartinib] will be used for this analysis) to the dose-normalized AUC_{inf} after the IV dose (data from the hot assay [i.e., ¹⁴C-quizartinib] will be used for this analysis).

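### The both-doses PK Evaluable Population would drop a subject with a usable oral profile but a missed or failed infusion from oral parameter summaries that do not need the IV dose

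*Combined protocol and SAP*

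**What the plan says.** Section 9.4.1 defines two PK populations. The PK Analysis Population serves concentration summaries and concentration-time profiles. The PK Evaluable Population serves parameters: "The PK Evaluable Population will be used for summaries of PK parameter estimates". Entry to the second set depends on both products: "An evaluable subject is defined as a subject who has received both the oral and IV microtracer IMPs", together with sufficient samples for plasma PK.

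Section 9.5.2.2 repeats the assignment and extends it from summary to calculation: "The PK Evaluable Population will be used for the calculation and summaries of the PK parameters listed in Section 9.5.2.1". The list in 9.5.2.1 includes plasma and whole-blood quizartinib and AC886, their metabolite-to-parent ratios, and Ae and Fe of quizartinib and AC886 in urine and feces, with Fe expressed against the oral dose.

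Other relevant text:

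- Section 4.3 sets the IV dose at 1/1200th of the oral dose so that the IV "microdose does not contribute significantly to the exposure following oral dosing".
- Section 9.2 enrolls 8 to obtain at least 6 evaluable subjects, "to allow for withdrawal or non-PK evaluability in up to 2 dosed subjects". Section 5.4 does not replace withdrawn subjects.
- The Safety Population in 9.4.2 is "all subjects who receive at least 1 dose of quizartinib", so the plan does use a one-dose criterion elsewhere.
- Sections 9.5 and 9.5.2.2 leave details of the populations to a SAP that is not part of the text supplied.

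**The concern.** The both-doses condition suits F, which is a ratio of oral to IV exposure. It does not suit endpoints defined on the oral dose alone, such as the plasma quizartinib parameters in 3.2 or the oral Ae/Fe and whole-blood parameters in 3.3. Suppose a subject takes the tablets, the infusion 4 hours later is missed or fails completely, and he is sampled to 504 hours. Under the rule as written he contributes concentrations but no parameters, although his oral profile is as informative as anyone else's.

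In a trial of 8 without replacement, each such subject is 12.5% of the data for these summaries. What is at stake is the precision of descriptive secondary and exploratory results. The primary endpoint is not at stake.

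**Working it through.** **1. The plan's own figure.** 8 enrolled − 2 lost = 6 evaluable, as in 9.2. There is no power calculation to reproduce.

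**2. Does any clause re-admit an oral-only subject?**

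- The PK Analysis Population covers concentrations and profiles. It does not cover the AUC, half-life, clearance or excretion parameters.
- The flexibility clauses in 9.4.1 add exclusions and flags only.
- The optional extra subset in 9.5.2.2 concerns only subjects with AUCextr above 20%.

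So no visible clause re-admits him. Kbp is the one unclear item. It is listed in 9.5.2.1, but 9.5.2.2 also places it in the paragraph on the PK Analysis Population ("Whole blood-to-plasma quizartinib and AC886 concentration ratios (Kbp) will also be calculated at each sampling time point"), so it is not counted as lost.

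**3. Which endpoints are touched?** From 3.2 and 3.3: plasma quizartinib 7, plasma AC886 6 (including the metabolite-to-parent ratio), whole-blood quizartinib 7, whole-blood AC886 5. The total is 7 + 6 + 7 + 5 = 25, plus oral Ae and Fe of quizartinib and AC886. These come from the same few profiles, so the count describes scope and not 25 separate losses.

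**4. Would an oral-only subject be comparable with the others?** The maximum IV share of oral quizartinib AUC is 50 µg / (60,000 µg × F). F is unknown, so values are assumed:

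| Assumed F | IV share |
|---|---|
| 1.0 | 0.083% |
| 0.5 | 0.167% |
| 0.25 | 0.333% |

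Missing the IV dose changes his oral exposure by a third of one percent at most over this range.

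**5. Precision lost.** The standard error of a mean log parameter relative to n = 8 is √(8/n). The 95% CI half-width in SD units is t(0.975, n−1)/√n.

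| n | SE ratio | Half-width (SD) | Half-width ratio |
|---|---|---|---|
| 8 | 1.000 | 0.8360 | 1.000 |
| 7 | 1.0690 (+6.9%) | 0.9248 | 1.106 (+10.6%) |
| 6 | 1.1547 (+15.5%) | 1.0494 | 1.255 (+25.5%) |

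The half-width is used only as a measure of precision. The visible text plans no confidence interval for these parameters.

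**6. How likely?** The documents give no infusion failure rate, so p per subject is assumed. P(at least one of 8) = 1 − (1−p)^8. P(at least two) = 1 − (1−p)^8 − 8p(1−p)^7.

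| Assumed p | At least one | At least two |
|---|---|---|
| 1% | 7.7% | 0.3% |
| 2% | 14.9% | 1.0% |
| 5% | 33.7% | 5.7% |

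These are upper bounds for the problem described, because the subject must also go on to give an adequate oral profile. The n = 6 row in step 5 needs two such subjects.

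**The case against.** A single common set is a defensible convention here. Section 4.2 presents the design as measuring IV and oral kinetics in the same individuals, and one set keeps N equal across tables. The event is also unlikely: a 5 mL, 15-minute infusion given by trained staff in a resident unit, with 9.3 expecting no compliance problem. A missed infusion need not leave a usable oral profile either. Section 6.4 requires a decision on whether a subject with a compliance violation may continue, and 7.1 lists significant protocol deviation among the grounds for withdrawal. There is no hypothesis test, and the final populations may be refined in the SAP or under the sponsor's non-compartmental guidelines, neither of which is visible.

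Much of this stands. It limits the priority and makes the probabilities upper bounds. It does not remove the rule, which the protocol states twice without a split by route; a SAP that follows it inherits the loss.

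A reader might infer that the answer is to split fully by route, with an IV set that does not require the oral dose. The documents argue against that. Section 4.2 gives the microdose with a therapeutic oral dose, near its expected Tmax, precisely to avoid dose-dependent kinetics at microdose exposure. The both-doses condition is therefore justified for the 14C parameters.

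A reader might also take the allowance of 2 in 9.2 as evidence that infusion failures are expected. It is a general allowance, and withdrawal or too few samples could exclude a subject from an oral set as well.

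**Conclusion.** The point holds in a limited form. The stated rule would remove an oral-only subject from oral quizartinib and AC886 parameter summaries for which the IV dose is not needed. With one such subject the standard error rises by 6.9% and the CI half-width by 10.6%; with two, by 15.5% and 25.5%. At assumed failure rates of 1% to 5% per subject, the chance is at most 7.7% to 33.7% for one or more cases and about 0.3% to 5.7% for two or more. No bias is expected if the failure is technical.

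Three stronger inferences are not supported:

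- That every PK parameter is lost. Kbp is ambiguous, and concentrations and individual profiles are retained.
- That the primary result is affected. F needs both doses under any rule, and its own exclusion is separate: "For the primary analysis, including calculation of absolute bioavailability (F), individuals having >20% AUCextr (%) will be excluded".
- That a partial infusion is wholly unaddressed. The definition in 9.4.1 specifies the 50 µg dose, 6.2.2 tolerates a different duration only if the full dose is given, and 9.4.1 allows exclusions and flags for deviations. Explicit wording would be clearer, but a route exists.

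This is a cheap improvement of low priority. If all 8 subjects receive both doses with adequate profiles, it changes nothing.

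**What to change.** In 9.4.1, add an oral parameter set: subjects who received the oral dose and have sufficient samples for the oral profile. Use it for unlabeled quizartinib and AC886 plasma and whole-blood parameters, their metabolite-to-parent ratios, and oral Ae/Fe.

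Keep the requirement that both doses were received for the 14C-quizartinib, 14C-AC886 and total-radioactivity parameters, and for F, which stays subject to the AUCextr exclusion above 20%.

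Refer to these sets in 9.5.2.2 and carry them into the SAP before it is known whether any infusion failed. Also show CL and CL/F on the both-doses set, so that the same-individuals comparison in 4.2 is preserved.

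The cost is a few sentences and one additional presentation of CL and CL/F, with no change to conduct, sampling or the primary analysis. The downside is that N may differ between oral and IV tables, which a footnote can explain.

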9.4.2. Safety Population

The safety analysis will be conducted using the Safety Population defined as all subjects who receive at least 1 dose of quizartinib.

9.5. Statistical Analysis

The statistical analysis plan (SAP) will be developed and finalized before database lock and will describe the subject populations to be included in the analyses, and procedures for accounting for

missing, unused, and spurious data. This section is a summary of the planned statistical analyses of the primary and secondary endpoints.

No formal interim analyses are planned for this study.

9.5.1. Safety Analysis

9.5.1.1. Adverse Events

Treatment-emergent adverse events are defined as new AEs that occur after the first dose of study drug. AEs occurring after Day 29 will not be considered TEAEs unless they are treatment-related. AEs will be coded using the Medical Dictionary for Regulatory Activities (MedDRA) dictionary (see Section 10.1.7.3). An AE will be assigned to the study day on which it started, even if it resolved on a subsequent day. The incidence of TEAEs will be summarized. The number and percentage of subjects reporting TEAEs will be calculated overall, by system organ class, and by preferred term.

Treatment-emergent adverse events, or AEs that are present prior to the first dose but which worsen in severity after the first dose of study drug, will be further summarized by common terminology criteria for adverse events (CTCAE) grade and relationship to study drug. Similarly, the number and percentage of subjects reporting treatment-emergent SAEs and related treatment-emergent SAEs will be tabulated, treatment-emergent AESIs, and TEAEs leading to discontinuation of study drug.

A by-subject AE (including treatment-emergent) data listing including but not limited to verbatim term, preferred term, system organ class, CTCAE grade, and relationship to study drug will be provided. Deaths, SAEs, AESIs, and AEs associated with study drug discontinuation will be listed.

9.5.1.2. Clinical Laboratory Evaluation

Descriptive statistics will be provided for the clinical laboratory results by scheduled time of evaluation, as well as for the change from baseline. The baseline value is defined as the last non-missing value before the initial administration of study drug. In addition, mean change from baseline will be presented for the maximum and minimum post-treatment values and the values at discharge from the clinical unit.

Abnormal clinical laboratory results will be appraised by the site physician where any results of clinical significance will be recorded as an AE, and graded according to National Cancer Institute - common terminology criteria for adverse events (NCI-CTCAE) Version 5.0, if applicable, and the grade will be presented in a by-subject data listing. A shift table, presenting the two-way frequency tabulation for baseline and the worst post-treatment value according to the CTCAE grade, will be provided for clinical laboratory tests. A listing of Grade 3 or 4 results will be generated.

9.5.1.3. Electrocardiograms

Descriptive statistics will be provided for the ECG measurements by scheduled time of evaluation, as well as for the change from baseline. The baseline value is defined as the last non-missing value before the initial administration of study drug. In addition, the number and

percentage of subjects with ECG interval values meeting the criteria will be tabulated (e.g., QTc \leq 450 ms, >450 to \leq 480 ms, >480 ms to \leq 500 ms, and >500 ms; changes from baseline of \geq 30 ms to <60 ms, and \geq 60 ms).

A listing of ECG data will be generated.

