11. History, or presence in the average of triplicate ECGs at screening and admission (Day -1), of any of the following cardiac conduction abnormalities:
 - QTcF > 450 ms.
 - Evidence of second- or third-degree atrioventricular block.

- Evidence of complete left or right bundle branch block.
- QRS or T wave morphology that could, in the Investigator's opinion, render QT interval assessment unreliable (confirmed with triplicate ECG).

12. Diagnosis or suspicion of long QT syndrome (including family history of long QT syndrome).
13. Presence or history of clinically severe adverse reaction to any drug.
14. History of any cancer, except non-melanoma skin cancer, or resected non-metastatic cancer with no evidence of disease accepted by the Investigator and Sponsor medical monitor.
15. History of moderate to heavy alcohol use defined as consumption of more than 21 units of alcohol per week for males, where 1 unit of alcohol equals $\frac{1}{2}$ pint of beer or a 25 mL shot of 40% spirit, and 1.5 to 2 units equal 125 mL glass of wine, depending on type, or significant history of alcoholism or drug/chemical abuse within the last 2 years.
16. A confirmed positive alcohol breath test at screening or admission (Day -1).
17. Loss of more than 400 mL blood during the 3 months before the trial (e.g., as a blood donor).

Physical Examination

18. Subjects who do not have suitable veins for multiple venipunctures/cannulation as assessed by the Investigator or delegate at screening.

Medication Use and Lifestyle

19. Current smokers and those who have smoked within the last 12 months. A confirmed positive urine cotinine test at screening or admission (Day -1).
20. Current users of e-cigarettes and nicotine replacement products and those who have used these products within the last 12 months.
21. Use of drugs with a risk of QT interval prolongation or TdP within 14 days of admission (Day -1) (or 5 drug half-lives, if 5 drug half-lives are expected to exceed 14 days).
22. Use of any drugs or substances known to be inhibitors or inducers of CYP3A4/5 within 28 days from the first dose or 5 half-lives, if known, of the drugs or substances, whichever is greater, prior to admission (Day -1) and during the study.

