7. WITHDRAWAL/DISCONTINUATION FROM THE STUDY

7.1. Subject Withdrawal/Discontinuation from the Study Drugs

This is a single dose study, therefore, after an individual subject has received a dose of IMP, withdrawal of that subject from further dosing is not possible. Subjects may discontinue from the study for any of the following reasons:

- Adverse event
- Withdrawal by subject
- Investigator decision
- Protocol deviation
- Study termination by Sponsor
- Other

Subjects will be monitored for the following criteria which may require their withdrawal from some or all study procedures if continuation is not in their best interests, except when the withdrawal is a result of withdrawal of consent:

- Experiencing a serious or severe AE including but not limited to:
 - QTcF of >500 ms or increase in QTcF interval of >60 ms from baseline (confirmed following a repeat ECG)
 - ALT concentration >3 × the upper limit of the reference range (confirmed following a repeat ALT blood test)
- Termination of the study
- Upon the subject's request (withdrawal of consent)
- Significant deviation from the protocol
- Concurrent illness that would adversely affect subject safety or data integrity or requirement for prohibited medication
- Evidence of current SARS-CoV-2 infection

The study will be halted, and the risk to other subjects evaluated if any of the following criteria are met:

- A serious adverse reaction (ie a SAE considered at least possibly related to the IMP administration) in one subject.
- Severe non-serious adverse reactions (ie severe non-serious AE considered as, at least possibly related to the IMP administration) in two subjects in the same cohort, independent of within or not within the same system organ class.

Relatedness to IMP will be determined by the Investigator.

If the study is halted, a temporary halt will be submitted to the MHRA and EC in the form of a substantial amendment. The study may be resumed or terminated; however, it will not be

resumed until a further substantial amendment to resume the study is submitted and approved by MHRA and EC.

The ARSAC Practitioner will also be informed of the temporary halt.

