9.5.1.4. Vital Signs

Descriptive statistics will be provided for the vital sign measurements by scheduled time of evaluation, as well as for the change from baseline. The baseline value is defined as the last non-missing value before the initial administration of study treatment. A listing of vital signs data will be generated.

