10.6. Appendix 6: Pharmacogenomic Blood Samples Collection, Processing, Storage, and Shipment

As part of this study, a genotyping blood sample will be taken from each subject on Study Day 1. This sample will be stored for possible future PGx analysis. At screening, all potential subjects should be presented with the standard ICF, which will include details of these procedures.

Details of PGx blood samples collection, processing, storage, and shipment will be contained in the CSPM.

10.7. Appendix 7: Allowable Time Windows for Pharmacokinetic Blood, Urine and Fecal Samples, Clinical Laboratory Safety Samples, and Vital Sign, and Electrocardiogram Assessments

Table 10.4: Acceptable Time Windows

Procedures (in order of collection)	Allowable Time Window	
	Pre-dose	Post-dose
ECG (pre-dose, 4, 24, 72 and 504 hours post-oral dose)	No more than 2 hours before oral dose; inclusive of at least 5 minutes of quiet rest in the supine position	No more than ± 15 minutes from the nominal post-dose time point (4 through 72 hours post-oral dose); inclusive of at least 5 minutes of quiet rest in the supine position
	Approximately 2 minutes between triplicate ECGs (i.e. 1 to 3 minutes allowed between each of the triplicate ECGs)	No more than ± 1 hour from the nominal post-dose time point (504 hours post-oral dose [discharge]); inclusive of at least 5 minutes of supine rest
Vital signs (pre-dose, 4, 24, 72 and 504 hours post-oral dose)	No more than 2 hours before oral dose; inclusive of at least 5 minutes of supine rest	No more than ± 15 minutes from the nominal post-dose time point (4 through 72 hours post-oral dose); inclusive of at least 5 minutes of supine rest
Hematology, Serum Chemistry (96 and 504 hours post-oral dose)	Not applicable	No more than ± 1 hour from the nominal post-dose time point
Coagulation (pre-dose, 96, and 504 hours post-oral dose)	No more than 2 hours before oral dose	No more than ± 1 hour from the nominal post-dose time point
Urinalysis (96 and 504 hours post-oral dose)	Not applicable	No more than ± 2 hours from the nominal post-dose time point

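### Does the last-non-missing-value rule reduce triplicate ECGs to a single baseline tracing and inflate QTcF change?

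*Combined protocol and SAP*

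**What the plan says.** Section 8.6.7 fixes the recording: "Triplet 12-lead ECGs (approximately 2 minutes apart) will be recorded for every subject". Table 10.4 (Section 10.7) gives the times, "ECG (pre-dose, 4, 24, 72 and 504 hours post-oral dose", and the spacing, "Approximately 2 minutes between triplicate ECGs (i.e. 1 to 3 minutes allowed between each of the triplicate ECGs". The Schedule of Events adds ECGs at screening and on Day -1, so each subject has three pre-dose occasions with three tracings each.

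The analysis is in Section 9.5.1.3: "Descriptive statistics will be provided for the ECG measurements by scheduled time of evaluation, as well as for the change from baseline". Baseline is defined there as "The baseline value is defined as the last non-missing value before the initial administration of study drug". The section also tabulates subjects by QTc level and by change from baseline (30 to under 60 ms, and 60 ms or more), with the categories given as examples. Section 9.5.1.4 uses nearly the same baseline sentence for vital signs: "The baseline value is defined as the last non-missing value before the initial administration of study treatment". Section 9.5.1.2 uses it for laboratory tests.

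Averaging is stated only for eligibility. Exclusion criterion 11 in Section 5.2 reads: "History, or presence in the average of triplicate ECGs at screening and admission (Day -1". Section 9.5 describes itself as a summary and defers detail to a SAP to be finalized before database lock. The combined document contains no separate SAP text.

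**The concern.** A baseline rule that suits one laboratory value per visit has been carried over to a measurement made three times within minutes. On a literal reading, the last value before dosing is the third pre-dose tracing, and the other two are discarded. Nothing says what happens to the post-dose triplicates either.

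ECG is a secondary safety endpoint, and Section 2.3.1 describes dose-dependent QT prolongation. A single tracing is noisier than a mean of three, so the choice affects the spread of QTcF change and can move a subject across the 30 ms line. With 8 subjects, one reclassification is 1/8 = 12.5 percentage points. Two analysts could therefore report different category counts from the same tracings.

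**Working it through.** **Inputs.** Three tracings per occasion (Section 8.6.7). The categories come from Section 9.5.1.3. The plan gives no QTcF SD, so there is no figure of its own to reproduce. Variances and true changes below are assumptions.

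**Model.** Let σw² be the tracing-to-tracing variance within an occasion and σb² the within-subject variance between occasions, both equal before and after dosing, with independent tracing errors. With n0 tracings averaged at baseline and n1 post-dose:

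Var(change) = 2σb² + σw²/n0 + σw²/n1

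- Means at both times (3, 3): 2σb² + (2/3)σw²
- Single baseline, mean post-dose (1, 3): 2σb² + (4/3)σw²
- Single at both times (1, 1): 2σb² + 2σw²

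**Ceilings.** With σb² = 0, the SD ratio against means at both times is √[(4/3)/(2/3)] = √2 = 1.414 for a single baseline, and √[2/(2/3)] = √3 = 1.732 for single tracings at both times. A simulation with 400,000 draws gave 1.414 and 1.733.

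**Effect of occasion-to-occasion variance.**

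| σb²/σw² | Single baseline only | Single at both times |
|---|---|---|
| 0 | 1.414 | 1.732 |
| 0.25 | 1.254 | 1.464 |
| 0.5 | 1.183 | 1.342 |
| 1 | 1.118 | 1.225 |
| 2 | 1.069 | 1.134 |
| 4 | 1.038 | 1.074 |

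The occasions compared run from pre-dose to 504 hours, so σb² = 0 is implausible and the first row is a limit only. The 1.41 also needs an analyst who averages post-dose triplicates but not the baseline. If neither is averaged, 1.41 is no longer the bound.

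**Chance that one post-dose reading is flagged at 30 ms or more.** This is 1 − Φ[(30 − d)/SD], where d is the true change and SD = √Var(change). The total SD of one tracing is s = √(σb² + σw²). Example: s = 10 ms, σb² = 0, single baseline, d = 10 ms gives SD = 10√(4/3) = 11.55 and z = 20/11.55 = 1.73, so the chance is 4.2%.

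| s (ms) | σb²/σw² | d (ms) | Means both | Single baseline | Single both |
|---|---|---|---|---|---|
| 10 | 0 | 0 | 0.01% | 0.5% | 1.7% |
| 10 | 0 | 10 | 0.7% | 4.2% | 7.9% |
| 10 | 0 | 20 | 11% | 19% | 24% |
| 10 | 1 | 0 | 0.5% | 1.0% | 1.7% |
| 10 | 1 | 10 | 4.2% | 6.1% | 7.9% |
| 5 | 0 | 10 | <0.01% | 0.03% | 0.2% |

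For the 60 ms line, the largest chance over s = 5, 8, 10 and d = 0, 10, 20 is 0.23% (single at both times, s = 10, d = 20: z = 40/14.14 = 2.83). At d = 0 it is about 0.001%.

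**Which reading the text supports.** Section 9.5.1.3 summarises by scheduled time and counts subjects, which presupposes one value per subject per time. The baseline rule then chooses among screening, Day -1 and pre-dose, or falls back to an earlier occasion if pre-dose is missing. That is the job it does for laboratory tests and vital signs. It leaves unstated how a triplicate becomes one value. Criterion 11 shows the convention the authors use when they need one value, and nothing in the document suggests discarding two tracings of three.

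**The case for a change.** The strongest case for a change is that the authors stated averaging for eligibility and so did not treat it as self-evident. Nothing carries it over to the analysis, and the generic baseline sentence could be copied into the SAP unchanged. The silence also covers post-dose values, where even the absolute QTc categories could be applied to any tracing, the last one or the mean. Under the least favourable assumptions (s = 10 ms, all within the triplicate, true change 10 ms), the chance that at least one of 8 subjects is flagged at 30 ms or more at one time point is 1 − (1 − q)⁸. That gives about 6% with q = 0.0072, 29% with q = 0.0416 and 48% with q = 0.0787. One sentence would settle it at no cost.

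Two things stand: the omission is real, and the arithmetic is right under its assumptions. But the argument shows only that a protocol summary lacks a detail. The large probabilities need an assumed 10 ms SD with no occasion-to-occasion variance, together with an analyst who ignores the purpose of triplicate recording. At s = 5 ms the per-reading chance at the same true change is at most 0.2%. If the SAP states the mean, nothing remains to be done.

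**Conclusion.** This is a gap that analysts fill sensibly, and it calls for no change to the plan. Section 9.5.1.3 does not say how a triplicate becomes one analysis value. Its wording fits selection of the last pre-dose occasion, the protocol's own precedent is the mean, and replicate handling is ordinary SAP content.

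If single tracings were used against expectation, the SD of QTcF change would rise by at most 1.41 times (baseline only) or 1.73 times (both times). For assumed between-to-within variance ratios from 0.25 to 4, the baseline-only figure is 1.25 down to 1.04. These bounds assume equal tracing variance before and after dosing and independent errors. The documents do not allow the actual value to be computed.

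Little depends on it. Section 9.1 states that no hypothesis is tested, and the ECG tables are descriptive in 8 subjects. The count at 60 ms or more is practically unaffected for true changes up to 20 ms. The withdrawal criterion in Section 7.1 already requires confirmation: "QTcF of >500 ms or increase in QTcF interval of >60 ms from baseline (confirmed following a repeat ECG". A listing of ECG data is planned, and the absolute bioavailability estimate does not use ECG data.
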